3.2.3 Primary Safety Endpoints

The primary safety endpoint is a change in best-corrected visual acuity (BCVA) that involves a loss of three lines or more from baseline.

4 Study Population and Duration of Participation

4.1 Dose Tolerability Test (Phase 1)

4.1.1 Inclusion Criteria

- Ages 65-90
- Female participants must be menopausal. Male participants are required to use contraception.
- Able to give informed consent
- For the study duration (15 days), the subject must remain in the country, remain within 4 hours of travel time (by car or airplane), have access to medical care if needed, and provide contact information so the subject can be reached as needed.

4.1.2 Exclusion Criteria

- Blood Pressure greater than 190/100 at the baseline visit
- Pulse greater than 100 at the baseline visit
- Acute and ongoing systemic infection
- History of dementia
- Participant has a condition that, in the opinion of the investigator, gives them an unstable medical status.
- Participant has geographic atrophy and the investigator believes the participant is a candidate for enrollment into Phase 2 of this trial.

4.1.3 Subject Recruitment

Subjects will be recruited from the investigator's site (Scheie Eye Institute of the University of Pennsylvania)

4.1.4 Duration of Study Participation

Subjects will participate in the ALA tolerability test for 15 days.

4.1.5 Total Number of Subjects and Sites

15 subjects will be recruited from a single site (Scheie Eye Institute of the University of Pennsylvania) for the ALA tolerability test.

4.1.6 Vulnerable Populations

No vulnerable populations will be involved with this study.

4.2 Randomized, double-blind placebo controlled trial (Phase 2)

4.2.1 Inclusion Criteria

- Age 55-90
- Diagnosis of geographic atrophy from age-related macular degeneration in the study eye. The largest GA lesion must be a minimum of 0.5 DA (1.25 mm²) and no more than 6 DA in size (15.0 mm²). GA is defined as one or more well-defined, usually more or less circular patches of loss of the RPE, typically with exposure of underlying choroidal blood vessels. If the GA is multifocal and the largest lesion is < 0.5 DA, then there should be at least 3 lesions ≥ 250 microns in greatest linear diameter.
- BCVA between 20/20 and 20/400 in the study eye.
- Female participants must be menopausal. Male participants are required to use contraception and cannot donate sperm during study participation.
- Presence of hyperfluorescence at the edge of GA on autofluorescence imaging.

CONFIDENTIAL

This material is the property of the University of Pennsylvania.

- Ability to give informed consent.
- If a subject has two eligible eyes, then both eyes can be enrolled into the study.
- Subject must have mailed back the medication bottle after the 10 day run-in phase, demonstrating that they have taken $\geq 80\%$ of the capsules.

4.2.2 Exclusion Criteria

- Evidence of ocular disease other than AMD in the study eye that may confound the study outcomes (e.g., History of myopic degeneration, choroidal neovascularization, central serous chorioretinopathy, severe diabetic retinopathy, uveitis, vitelliform dystrophy, or macular edema).
- Presence of geographic atrophy that is already touching clearly defined beta peripapillary atrophy or is already touching the optic disc. Beta peripapillary atrophy is defined as peripapillary atrophy in which either the sclera or choroidal vessels are clearly visible.
- Any history of intravitreal injection in the study eye for AMD or choroidal neovascularization. However, if a subject develops choroidal neovascularization in the study eye *during* the study, then the subject will receive the standard of care intravitreal injection treatments per the investigator. The subject will continue to stay in the study. Treatment of CNV or other diseases in the non-study eye is at the investigator's discretion.
- History of intravitreal injection of any agent (e.g., triamcinolone) other than anti-VEGF in the study eye within the last four months prior to study enrollment.
- History of laser treatment (including photodynamic therapy) to the macula for the study eye.
- History of intraocular surgery within 90 days for the study eye.
- History of anterior segment laser (laser peripheral iridotomy, laser to trabecular meshwork, YAG capsulotomy) within 90 days for the study eye.
- Media opacity (corneal scar, cataract) that would prevent adequate fundus imaging for the study eye.
- Any history of participation in another therapeutic clinical trial for GA.
- Participation currently or within the past 30 days in another therapeutic clinical trial in which a systemic or ocular study medication is received by the subject.
- GA in the study eye due to a cause other than AMD
- History of prior use of ALA.
- AREDS (Age Related Eye Disease Study) vitamins taken at standard doses are not considered an exclusion criterion. Taking any of the individual components of the AREDS vitamins at doses consistent with the AREDS formula (instead of taking the AREDS vitamins) is not considered an exclusion criterion. Taking a standard multivitamin is not considered an exclusion criterion. However, the multivitamin should not contain alpha lipoic acid (also known as thioctic acid).
- Taking antioxidant supplements other than a standard multivitamin (such as bilberry, vitamin C that is not part of a multivitamin or taken at higher doses than the AREDS formula, vitamin E that is not part of a multivitamin or taken at higher doses than the AREDS formula, or other similar antioxidants) within one month of enrollment is an exclusion criteria; these patients should discontinue the antioxidant supplement one month before enrollment in order to participate. Taking a supplement that has antioxidant potential that is recommended by a physician as standard-of-care medical management is not an exclusion criterion.
- Participant has a condition that, in the opinion of the investigator, would preclude participation in the study for 18 months (e.g., unstable medical status including blood pressure and glycemic control, unstable psychiatric history, moving and not able to return for all planned study visits).
- History of a formal diagnosis of dementia by a neurologist.
- History of gastric ulcer within the past 5 years.
- History of irritable bowel syndrome within the past 5 years.

CONFIDENTIAL

- History of severe, chronic gastric reflux such that it causes discomfort several times a week (within the past 6 months).
- Male subjects who refuse to use acceptable contraceptive methods.

4.2.3 Subject Recruitment

Subjects will be recruited from the investigators' clinical practice as well as from referring clinical practices on site. We may plan to utilize Penn media services to increase subject recruitment.

4.2.4 Duration of Study Participation

Subjects will participate in the study for an 18 month period (from the time of randomization).

4.2.5 Total Number of Subjects and Sites

Recruitment for screening visits will end after 50 subjects are randomized. If there are subjects that were already screened and consented at the time the 50th subject is randomized, then eligible patients will be allowed to proceed to the Run-In period and randomization (if the subject passes the Run-In requirements). This would not be expected to be more than a few subjects. It is expected that approximately 10-15 subjects per site will be enrolled in order to produce 50 evaluable subjects.

4.2.6 Vulnerable Populations

No vulnerable populations will be involved with this study.

5 Study Intervention

Please refer to sections 6.2.

5.1 Description of study medication

Study medication is comprised of ALA 600mg capsules or placebo capsules.

5.2 Intervention Regimen

Subjects will take one 600mg capsule of ALA (or placebo) once daily with a meal for 2 weeks and then increase to two 600 mg capsules of ALA (or placebo) once daily with a meal for the remainder of the 18 month period of the study.

For the tolerability test (Phase 1), see section 3.1.1. The 800 mg oral ALA dose will consist of two 400 mg capsules of ALA.

5.3 Receipt

The ALA is provided by Pure Encapsulations (Sudbury, MA). It is received, stored, handled, and distributed to investigators by the University of Pennsylvania Investigational Drug Service.

5.4 Storage

Active and placebo capsules will be stored, labeled and distributed to Investigators or directly mailed to the subject's home by the University of Pennsylvania Investigational Drug Service. All drugs (active drug and placebo) must be stored at room temperature.

5.5 Preparation and Packaging

In order to maintain the study blind, the Perelman School of Medicine Investigational Drug Service (IDS) will manufacture a placebo capsule to match the active ALA 600mg capsule provided by Pure Encapsulations Inc. A white, semi-opaque Size 0 pharmaceutical grade capsule shell will be filled with a combination of microcrystalline cellulose NF (approximately 600mg) plus trace amounts of coloring agents in order to closely mimic the appearance of the powder inside the active ALA capsule. Both placebo and ALA will be light yellow.

For dispensing, capsules will be hand-counted and placed into white opaque Type 2 HDPE

CONFIDENTIAL

pharmaceutical rounds which comply with USP<671> specifications, in either 120mL or 250mL capacity, with a PS-22 tamper-evident liner and a child-resistant cap. A non-child-resistant cap may be provided to the clinician on request, for the subject to switch to after dispensing if he/she has difficulty opening bottles and has no young children living at home. Bottles will include labeling compliant with FDA regulation, 21 CFR 312.6.

5.6 Blinding

Blinding only applies to Phase 2 of this protocol. A master file of subject assignments will be kept by the data coordinating center. The research team and the subject will be blinded and will not know the investigational product contained each capsule. The blind may be broken in the case of an emergency.

5.7 Administration and Accountability

When dispensing bottles of study run-in capsules, a member of the study team will record information onto the drug inventory logs. The Investigational Drug Service provides an “ALA for GA Study Medication Ordering, Distribution, and Accountability Manual” to each clinical center. Outdated supplies will be recalled by the Investigational Drug Service or destroyed on site and replacement supplies provided.

At each visit after the baseline visit and when run-in bottles are returned, unused study drug will be collected. Returned drug must be stored in the returned bottle in a secured location. The date the bottles are returned are noted on a drug accountability log.

All drug storage facilities and medication dispensing and collection records will be made available for inspection.

5.8 Subject Compliance Monitoring

Each Investigator must make visits as pleasant as possible by minimizing wait time and providing comfortable waiting and examination facilities. The Investigator for each Clinical Center will continually educate the subjects as to the nature of the study, the need for the subject’s continued participation, and answer questions concerning geographic atrophy and the use of ALA.

In Phase 2, subjects will be contacted to remind them of a follow up visit within the week of the appointment. The contact can be by telephone or email and a subject response is necessary. To ensure subject compliance for scheduled visits, early morning, evening, or weekend hours may be provided. Every effort must be made by the Investigator to remain in contact with subjects, even if they do not want to return to be examined or follow the protocol. After subjects enrolled in Phase 2 are randomized, they will be contacted at week 2 and months 1, 3, 9, and 15 months to ensure study drug compliance and to inquire about any difficulties with the study drug.

If a subject cannot tolerate the study medication (ALA or placebo) because of gastric reflux or symptoms thought to be from gastric reflux, they will be encouraged to prevent their symptoms by taking an over-the-counter gastrointestinal medication for reflux such as ranitidine or omeprazole. The investigator will make the determination that the symptoms are consistent with reflux and make the recommendation for gastrointestinal prophylaxis on a case-by-case basis. The investigator may choose to involve an internist in making this decision. Any use of gastrointestinal prophylaxis medications will be recorded. If ranitidine is desired to treat such symptoms at no cost to the subject because of reflux presumed to be related to the study medication, then a prescription may be sent (fax/email) to the UPenn IDS and the ranitidine will be mailed to the subject. The study’s Clinical and Scientific Expert must be notified and approve of this action within one week and prior to sending the ranitidine prescription to the Penn IDS.

If a subject cannot tolerate the study medication (ALA or placebo) for the reasons detailed below, then the subject will be asked if he/she is willing to take one capsule twice daily instead of two capsules once daily:

- there are uncomfortable gastrointestinal symptoms that do not resolve with medication for reflux,
- there are gastrointestinal symptoms and the subject does not want to take any prophylactic gastrointestinal medication, or

CONFIDENTIAL

- there are other symptoms causing intolerance of the study dose

If the subject cannot tolerate or does not want to take one capsule twice daily, then the subject will be asked if he/she is willing to take one capsule once daily. If the subject cannot tolerate one capsule once daily or does not want to take one capsule once daily, then the subject will be asked to at least remain in the study. All changes to the schedule of study medication dosing will be documented.

The study subjects will be asked to provide urine samples at the 12 months study visit. The urine will be tested for a metabolite of ALA to determine the subject's compliance. The samples will be tested in the Metabolomic Core Laboratory directed by [name] at the Children's Hospital of Philadelphia (CHOP). Please follow the instructions below for shipping of urine samples from each site to the Scheie Eye Institute lab for storage before analysis.

Instructions for shipping and handling of urine analysis samples:

Samples must be frozen (in a -20 °C freezer, shipping labels will be provided, samples must be shipped frozen on dry ice via overnight carrier to:

[name] Laboratory
University of Pennsylvania
[name]
[name]
[name]

Contact Information:

Office: [contact]

Email: [contact]

Urine samples will be stored in a freezer in the [name] Laboratory at -20 °C or less. The temperature of this freezer should not drop below -20 °C.

The collected urine samples will be transferred on dry ice to:

The Children's Hospital of Philadelphia (CHOP) Abramson Research Center (ARC) 5TH Floor,
[name]
[name]
[name]

Contact information:

[name],

Email: [contact]

[contact]

or

[name],

Email: [contact]

[contact]

[contact]

For questions please contact:

[name]

Metabolomic Core Director

Email: [contact]

The samples will be transferred from the [name] lab to the [name] lab in a total 2-3 batches with the first batch sent after 35% or more of samples have been collected.

CONFIDENTIAL

5.8.1 Return or Destruction of Investigational Product

Completion of the study is met when a study subject completes the follow-up visits as specified by the subject's allotted study Phase. At this point, all remaining study medication will be collected. The amount of remaining capsules (if any) will be counted by study team personnel and reported to the coordinating center. The remaining study medication will be disposed of at the clinical site.

6 Study Procedures, Phase 1

6.1 Screening

At the baseline screening visit, a complete medical history list will be elicited from the subject and extracted from available medical records. Data to be collected include: age, gender, ethnicity, medical history, medications, allergies, ocular diseases, ocular surgeries, and non-ocular surgeries. A blood pressure and pulse will also be checked and documented at this visit. Based on all of this data, it will be confirmed that the patient meets all inclusion and exclusion criteria.

After signing the informed consent document, the ALA will be dispensed to the subject. Data will be directly collected onto case report forms, which will be considered the source data.

6.2 Study Intervention and Follow-up Phase

15 subjects (ages 65-90) will take 600 mg of oral ALA once daily with a meal for 5 days. This medication will be placed in a red-banded medication bottle (#1) with clear instructions. Each subject will be monitored by the study physician, who will record a history of any side effects or tolerability issues, including a complete review of systems. If well-tolerated, each subject will then take 800 mg of oral ALA once daily with a meal for 5 days. This medication will be placed in a green-banded medication bottle (#2) with clear instructions. Each subject will be monitored by the study physician who will record a history of any side effects or tolerability issues, including a complete review of systems. If 800 mg of oral ALA is well-tolerated, then these subjects will be asked to take 1200 mg of oral ALA daily again for 5 days with a concurrent meal. This medication will be placed in a blue-banded medication bottle (#3) with clear instructions. Each of these subjects will be monitored by the study physician who will record a history of any side effects or tolerability issues, including a complete review of systems. Patients will be contacted by the study physician every 5 days to check on tolerability issues and to determine if the patient can safely proceed to the next dose of ALA.

6.3 End of Study

At the time of the final phone call, the subject will be asked to discontinue the ALA. A final review of systems will be recorded. If there are no urgent issues, then the subjects will be asked to maintain continued care with their primary care physician and ophthalmologist.

The enrolled subjects will be provided an envelope (with postage cost already paid). This envelope will be mailed to the subject's home or given to him/her at the time of their enrollment visit. Using the envelope, the subject will be asked to mail all of the study medication bottles to the Scheie Eye Institute. There will be documentation of the received medication bottles and the amount of any unused study medication within them. Unused study medication will then be destroyed at the Scheie Eye Institute.

6.4 Unscheduled Visits

Unscheduled visits will be handled as typical standard of care visits by the treating ophthalmologist. Any exams and tests at unscheduled visits will be billed to the subject's insurance per the usual practices of that ophthalmologist. At the next scheduled study phone call, any adverse events related to the need for the unscheduled visits will be recorded. If there is a significant change in exam or a new diagnosis noted at the time of the unscheduled visit (i.e. new choroidal neovascularization, retinal vein or artery occlusion, vitreous hemorrhage, etc.) the Sponsor will be notified.

CONFIDENTIAL

6.5 Subject Withdrawal

Subjects may withdraw from the study at any time without impact to their care. They may also be discontinued from the study at the discretion of the Investigator for lack of adherence to intervention or study procedures or visit schedules, AEs, or due to other concerns. The Investigator or the Sponsor may withdraw subjects who violate the study plan, or to protect the subject for reasons of safety or for administrative reasons. It will be documented whether or not each subject completes the clinical study.

The enrolled subjects will be provided an envelope (with postage cost already paid). This envelope will be mailed to the subject's home or given to him/her at the time of their enrollment visit. In the event of subject withdrawal, the subject will be asked to mail all of the study medication bottles to the Scheie Eye Institute using the provided envelope. There will be documentation of the received medication bottles and the amount of any unused study medication within them. Unused study medication will then be destroyed at the Scheie Eye Institute.

7 Study Procedures, Phase 2

	Baseline Visit	6 months visit	12 months visit	18 months visit
EVA/ETDRS Refraction	X	X	X	X
Distance Corrected Near Visual Acuity (ETDRS)	X	X	X	X
Dilated Exam	X	X	X	X
Fundus Photos	X	X	X	X
Autofluorescence	X	X	X	X
OCT	X	X	X	X
Pulse, BP, BW	X	X	X	X
Urine Test			X	
Medical Review	X	X	X	X
Ocular Surface Disease Index	X	X	X	X

7.1 Screening (at baseline)

At the baseline screening visit, the informed consent document is signed by the subject. A complete medical history list will be elicited from the subject and extracted from available medical records. Data to be collected include: age, gender, ethnicity, medical history, medications, allergies, ocular diseases, ocular surgeries, and non-ocular surgeries. The subject will be given the option of completing the Ocular Surface Disease Index (OSDI).⁴⁷ A dilated eye examination will be performed. A blood pressure, pulse, and body weight will also be checked and documented at the baseline, 6 month, 12 month, and 18 month visit as part of a routine safety assessment. Based on all of this data, it will be confirmed that the subject meets inclusion and exclusion criteria.

Run-In Period: The subject will be mailed a medication bottle with the instructions to take one capsule once daily for 10 days and a form to record the starting and stopping dates. The medication bottle will contain the placebo but the subject will not be informed that the medication bottle contains placebo or ALA. After taking the capsule for 10 days, the subject will mail the medication bottle, including any remaining capsules, and form back to the clinical site using a postage-paid envelope provided at the time of the baseline screening visit. Those subjects that have demonstrated compliance by taking $\geq 80\%$ of the provided capsules and mailing the medication bottle within 40 days of the screening visit will now have met all inclusion and exclusion criteria. The subject will then be randomized and study medication will be mailed to the subject by the Penn IDS (see section 3.1.1 Allocation to Intervention Group). If an investigator did not receive a mailed medication bottle but believes the subject followed instructions and the medication bottle was lost in the mail, then that subject may get screened again for the study. In this instance, the subject will have to repeat the screening visit and the run-in period.

CONFIDENTIAL

Subjects that participated in the Run-In but did not demonstrate an ability to take $\geq 80\%$ of the capsules will be notified within two weeks that they cannot continue in the study and that they received placebo capsules during the Run-In. Subjects that continue to randomization will be informed after the study is completed that they received placebo capsules for the Run-In and whether they were randomized to placebo or ALA.

After signing the informed consent document and within 45 days before study treatment administration, all screening procedures, including OCT, FAF, fundus photography, BCVA, and the 10 day run-in phase must be performed.

Data will be directly collected onto case report forms, which will be considered the source data. There is no restriction on the number of subjects to be enrolled by a particular site.

7.2 Study Intervention Phase

7.2.1 6 Month, 12 Month, and 18 Month Visits

Fundus photographs, OCT and FAF images will all be collected at enrollment (baseline), 6, 12, and 18 month visits only. Both eyes will be imaged. These will be collected by ophthalmic photographers certified for clinical trial imaging. The Scheie Eye Institute Reading Center will provide detailed grading of FAFs, color fundus photographs, and OCTs for determination of study outcomes. Color fundus photographs, FAF and OCT images will be submitted to the Scheie Image Reading Center at enrollment (baseline), 6, 12, and 18 months. At each of these visits, the subject will be given the option of completing the Ocular Surface Disease Index (OSDI).⁴⁷

Study visits must fit the recommended time frame as much as possible. All follow-up study visits must at least be within 3 months (+/- 3 months) of the recommended date of the study visit.

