Intervention Phase

The Coordinating Center is responsible for random assignment of patients to one of the two treatment groups. Random treatment allocation schedules will be generated using a randomized block design and stratified by clinical center. All baseline procedures must be performed within 40 days of the day of randomization.

For subjects who have successfully completed the run-in phase, the clinical site will inform the Coordinating Center that that all inclusion and exclusion criteria have been met. Coordinating Center staff will issue the next randomized treatment assignment from the clinical site's schedule for the patient. A Coordinating Center staff member notifies the clinical site Investigator that the randomization has been completed and the Investigator will fax/send a prescription for study medication (ALA or placebo), signed by the Principal or Sub-Investigator, to the University of Pennsylvania's Investigational Drug Service (IDS). A Coordinating Center staff member will notify IDS of the treatment assignment.

Once IDS receives both the prescription from the Investigator and the treatment assignment from the Coordinating Center, IDS will send a supply of study drug to the subject's home. Subsequent study medication also will be mailed by IDS directly to the subject's home.

For both study Phases, prior to starting the medication, the subject will be instructed on how to take the medication, and what signs and symptoms to monitor and report. For Phase 2 of the protocol, each subject will be contacted approximately two weeks after randomization to verify that the study drug has been received and that each subject is taking the study medication per instructions.

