8.1 Primary Endpoint

For Phase 1 of this protocol, the primary endpoint is the percent of adverse events that develop in the study group at each studied dose of ALA.

For Phase 2 of this protocol, the primary endpoint is the mean rate of change of the area of GA in the study eye from baseline to 18 months (from the time of randomization) as evaluated by fundus autofluorescence.

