8.4 Statistical Methods

Phase 1: Percentages of adverse events will be calculated.

Phase 2: As a preliminary analysis, the mean change in the total area of GA within study eyes over 18 months (from the time of randomization) will be compared between eyes receiving the active ALA dose and placebo supplementation; a square root transformation will be applied to the area measurements to mitigate the dependence of growth rate on initial size.⁵³⁻⁵⁴ Also, mean change in visual acuity over 18 months, the proportion with a decrease of 15 letters (3 lines) of visual acuity, and the proportions with serious adverse events will also be compared. Variants of the independent t-test and chi-square tests of proportions that account for the correlation between eyes of subjects who have two study eyes will be used to make comparisons.

The main analysis for comparing treatment groups will compare the rates of change in total area of GA using a mixed effects linear model. Use of this model allows including all patients in the analysis and requires less stringent assumptions than a complete cases analysis regarding the association of

CONFIDENTIAL

missingness with the outcome variable and does not introduce bias into the estimation of the slope parameter as a “last observation carried forward (LOCF)” approach does when area changes with time. Both subject and eye will be considered random effects. A sensitivity analysis using multiple imputation for missing values will be used for the analysis of mean change between baseline and 18 months and for the mixed effects linear model of total area.

Similar analytic methods using mixed effects models will be used for the other outcome measures.

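### With ±3-month visit windows, change in GA area should be scaled to the actual interval between images; 8.4 leaves the 18-month change unscaled and the mixed model's time variable undefined

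*Combined protocol and SAP*

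**What the plan says.** **Timing of images.** Section 7.2.1 asks that visits keep to schedule as far as possible, then sets the limit: "All follow-up study visits must at least be within 3 months (+/- 3 months) of the recommended date of the study visit". The 18-month image can therefore fall anywhere from month 15 to month 21. For baseline, 3.1.1 states: "All baseline procedures must be performed within 40 days of the day of randomization". Section 7.1 sets a second limit, counted to first treatment: "within 45 days before study treatment administration, all screening procedures, including OCT, FAF, fundus photography, BCVA, and the 10 day run-in phase must be performed".

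**Endpoint.** Section 8.1 defines a rate: "the primary endpoint is the mean rate of change of the area of GA in the study eye from baseline to 18 months". The 18-month point is dated from randomisation, whereas the change starts at the baseline image.

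**Analysis.** Section 8.4 begins: "As a preliminary analysis, the mean change in the total area of GA within study eyes over 18 months", on the square-root scale, compared between arms with t-test variants. It then names a main analysis, a linear mixed model comparing rates of change. The Study Summary gives only the first of these as the Phase 2 efficacy comparison. Section 8.2 adds absolute and relative change in lesion area on FAF and on colour photographs.

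Nowhere is a change divided by the interval over which it occurred. Nowhere is the model's time variable defined, either as actual dates or nominal months, or by its time zero.

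**The concern.** GA lesions keep enlarging, so the change seen between two images depends on how far apart they were taken. If the month-12 image is taken at month 9 and the month-18 image at month 21, they are 12 months apart but labelled 6. A t-test of unscaled 18-month change treats a 15-month and a 21-month interval as the same exposure.

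Two things are at stake. The first is avoidable noise in a trial expecting about 42 subjects after dropout. The second is a possible artefact: if one arm attends later on average, its extra growth is read as a treatment effect. Section 8.3 contemplates halting if observed growth is greater on ALA than on placebo, so a shift in that direction could affect the decision. A mixed model avoids both problems if it is given actual dates, but 8.4 does not say that it will be.

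**Working it through.** **Inputs.** From 8.3: 50 subjects, 15% dropout, one-sided 90% confidence, example growth of 0.40 mm (placebo) and 0.32 mm (ALA), SD of annual growth 0.20 mm. The growth rates are taken as per year, following the SD. From 3.1: 1:1 allocation. From 7.2.1: ±3 months. From 3.1.1 and 7.1: 40 and 45 days. Growth is assumed linear on the square-root scale. The timing distributions are illustrative, since the documents give none.

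**1. The plan's own figure.** Subjects per arm: 50 × 0.85 / 2 = 21.25. Half-width in SD units: 1.2816 × √(2/21.25) = 0.393, or 0.400 with the t distribution. The stated 0.4 reproduces. The example effect is (0.40 − 0.32)/0.20 = 0.4.

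**2. Range within the window.** Placebo growth is 0.40 × 1.25 = 0.50 mm at month 15 and 0.40 × 1.75 = 0.70 mm at month 21, a spread of 0.20 mm. The example difference at 18 months is 0.08 × 1.5 = 0.12 mm. These are the window extremes, not typical visits.

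**3. Noise in the unscaled change.** With rate mean m, rate SD s and elapsed time T:

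Var(change) = E[T]²s² + m²Var(T) + s²Var(T).

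Without timing variation this is (1.5 × 0.20)² = 0.0900. For visits uniform over ±3 months, Var(T) = 0.5²/12 = 0.0208 year².

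- At m = 0.40 the added variance is (0.16 + 0.04) × 0.0208 = 0.00417, or 4.6% (SD +2.3%).
- At m = 0.32 it is (0.1024 + 0.04) × 0.0208 = 0.00297, or 3.3% (SD +1.6%).

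At m = 0.40, the 0.4 effect size becomes 0.391 and the half-width goes from 0.393 to 0.402. With a timing SD of 1 month the variance rises 1.5% (SD +0.8%). With every visit at a window edge it rises 13.9% (SD +6.7%).

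**4. Shift if mean timing differs by arm.** One month at 0.40 mm/year is 0.40/12 = 0.033 mm, and 0.033/0.12 = 28%. Half a month gives 0.017 mm (14%). If the later arm grows at 0.32 mm/year, one month is 0.027 mm (22%).

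**5. Mixed model, if nominal months were used.** Per-subject slopes were simulated with uniform windows, baseline 0–45 days early, measurement error 0.05–0.10 mm and a true rate of 0.40.

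| | Nominal time | Actual time |
|---|---|---|
| Mean slope | 0.415 | 0.400 |
| SD of slopes | 0.217–0.231 | 0.205–0.218 |
| Mean slope, follow-up 1 month late | 0.435 | 0.400 |

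Nominal coding overstates the rate by about 4% and raises its SD by about 6%, much of which is the same change of scale. A one-month lag in one arm creates a difference of 0.435 − 0.415 = 0.020 mm/year, 25% of 0.08. With actual time there is none.

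**6. Baseline lag.** Against 18 months (548 days), 40 days is 7.3% and 45 days is 8.2%. Both are maxima and apply to both arms.

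**The case against.** The strongest reply is that the unscaled change is not the main comparison. Section 8.4 calls it preliminary and rests the main analysis on rates from a mixed model, which can take irregular times directly. A reader might infer that the primary comparison ignores elapsed time, or that nominal months will be used. The documents support neither: on the model's time variable they are silent. This part of the reply stands, though the Study Summary lists only the unscaled change, and 8.4 extends its multiple-imputation sensitivity analysis to it.

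The reply also holds that the noise is small, since 7.2.1 asks for visits on schedule and 5.8 provides reminders and flexible hours. That stands too.

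A reader might further infer a bias in favour of ALA. That needs mean timing to differ between randomised, blinded arms, and no timing data by arm are given. Section 8.3 expects that about 25% of the ALA arm may not tolerate 1200 mg, but nothing links intolerance to later visits. If it did delay them, the extra growth would count against ALA.

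Finally, the baseline lag might be read as a source of between-arm bias. It is not, because it precedes treatment and the same limits apply to both arms.

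**Conclusion.** The point holds as a modest, inexpensive improvement to the analysis. The preliminary 18-month comparison and the change endpoints in 8.2 are unscaled although the endpoint is a rate, and the main model's time variable is not stated.

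The cost in precision is about 4% in variance (2% in SD) if visits spread evenly over the window, and less if they cluster near target. Bias is conditional: 0.033 mm, or 28% of the 0.12 mm example difference, for each assumed month of difference in mean timing between arms. Under nominal timing, the baseline lag slightly mis-scales the rate and favours neither arm.

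These sizes rest on the example rates in 8.3 read as annual, linear growth on the square-root scale, and assumed timing distributions. They do not show that the main analysis is invalid or that a timing difference between arms should be expected.

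**What to change.** In 8.4:

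- Define time in the mixed model as years from the actual baseline FAF date to each actual FAF date.
- In the preliminary test, compare 18-month change divided by that same interval.
- Use the same definition for absolute and relative change on FAF and, with the colour-photograph dates, for the colour-photograph rate and change endpoints.
- Report the timing of visits by arm.

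Align the Study Summary with this wording. Visit windows and procedures stay unchanged. The cost is a few lines of text and no new data, assuming image dates are recorded with the images or on the CRF. Section 10.2 says that dates entered are checked, but does not name image dates.
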